8.11. Creatinine Clearance/Level

The creatinine level/clearance will be calculated using well-accepted Cockcroft-Gault equation. The formula allows the creatinine clearance to be estimated from the serum creatinine in a patient with a stable serum creatinine. The expression read as follows:

$$\text{For males: } CrCl[mL/min] = \frac{(140 - \text{age}[\text{years}] * \text{weight}[\text{kg}])}{\text{serum creatinine } [\mu\text{mol/L}]} \times 1.228$$

$$\text{For females: } CrCl[mL/min] = \frac{(140 - \text{age}[\text{years}] * \text{weight}[\text{kg}])}{\text{serum creatinine } [\mu\text{mol/L}]} \times 1.044$$

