8.3.1. Inclusion Criteria

A patient must meet all of the following inclusion criteria to be eligible for enrollment in this study:

- 1. Has provided written informed consent.
- 2. Has histologically confirmed non-resectable, metastatic gastric adenocarcinoma including adenocarcinoma of the gastroesophageal (GE) junction as defined by the American Joint Committee on Cancer (AJCC) staging classification (7th ed., 2010). Documentation of histology of the tumor (primary or metastasis) will be required prior to enrollment. Gastroesophageal junction involvement must be documented by endoscopic, radiologic, surgical or pathology report.
- 3. Has previously received at least 2 prior regimens (at least 1 cycle per regimen) for advanced disease and were refractory to or unable to tolerate their last prior therapy:
 - a. Prior regimen(s) must have included a fluoropyrimidine, platinum, and either a taxane- and/or irinotecan-containing regimen; patients whose tumors are HER2-neupositive (HER2+) must have received prior anti-HER2+ therapy if available.
 - b. Patients have progressed based on imaging during or within 3 months of the last administration of their last prior regimen.
 - c. Patients who have withdrawn from their last prior regimen due to unacceptable toxicity warranting discontinuation of treatment and precluding retreatment with the same agent prior to progression of disease will also be eligible to enter the study.
 - d. Patients who have received postoperative adjuvant chemotherapy or chemoradiotherapy, and had recurrence during or within 6 months of completion of the adjuvant chemotherapy are allowed to count the adjuvant therapy as one prior regimen for advanced disease. Patients who have received pre- and post-operative adjuvant chemotherapy, and had recurrence during or within 6 months of completion of the adjuvant chemotherapy are allowed to count the adjuvant therapy as one prior regimen only if the same regimen was administered both pre- and post-operatively.
- 4. Has measureable or nonmeasurable disease as defined by RECIST 1.1 criteria.
- 5. Is able to take medications orally (ie, study drug must not be administered via a feeding tube).
- 6. Is ≥ 18 years of age (≥ 20 years for patients in Japan).

- 7. Has an ECOG performance status of 0 or 1 CCI at time of randomization.
- 8. Has adequate organ function as defined by the following criteria:

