 - a. Absolute neutrophil count (ANC) of $\geq 1,500/\text{mm}^3$ (ie, $\geq 1.5 \times 10^9/\text{L}$ by International Units [IU]).
 - b. Platelet count $\geq 100,000/\text{mm}^3$ (IU: $\geq 100 \times 10^9/\text{L}$).
 - c. Hemoglobin value of ≥9.0 g/dL prior to randomization based on measurements obtained 2 weeks or more after last transfusion received.
 - d. Aspartate aminotransferase (AST; SGOT) and alanine aminotransferase (ALT; SGPT) \leq 3.0 × upper limit of normal (ULN); if liver function abnormalities are due to underlying liver metastasis, AST (SGOT) and ALT (SGPT) \leq 5 × ULN.
 - e. Total serum bilirubin of $\leq 1.5 \times ULN$ (except for Grade 1 hyperbilirubinemia due solely to a medical diagnosis of Gilbert's syndrome).
 - f. Serum creatinine $\leq 1.5 \text{ mg/dL}$.
- 9. Is willing and able to comply with scheduled visits, treatment plans, laboratory tests, and other study procedures.
- 10. Women of childbearing potential must have a negative pregnancy test (urine or serum) within 7 days prior to starting the study drug. Both males and females must agree to use effective birth control during the study (prior to the first dose and for 6 months after the last dose) if conception is possible during this interval. Female patients are considered to not be of childbearing potential if they have a history of hysterectomy, or are postmenopausal defined as no menses for 12 months without an alternative medical cause. For both males and females, see Section 8.8.3 for definitions of contraceptive methods considered effective for this protocol.

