8.12. Renal Function

The creatinine level/clearance will be used to identify the renal function. For the purpose of the present SAP the following subdivision will be used (round the calculated result for the creatinine clearance to the nearest whole number before application of the table below):

Renal Function	Creatinine Clearance (CrCl)
Normal	≥ 90 mL/min
Mild Impairment	60-89 mL/min
Moderate Impairment	30-59 mL/min
Severe Impairment	≤ 29 mL/min

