9.3. Demographic and Baseline Characteristics

The demographic and baseline characteristics will be summarized. The list of characteristics that will be summarized include but are not limited to the following:

- Gender
 - Age (years) (#)
 - Age group 1 (<65 years, ≥65 years)
 - Age group 2 (3 groups: (<65 years, 65≤ - <75, 75≤ years)
 - Race (White, Black, Asian, American Indian or Alaska Native, Native Hawaiian or Other Pacific Islander, Not Collectable, Other)
 - Race Group (White, Asian, Other)
 - Ethnicity (Hispanic or Latino, Not Hispanic or Latino, Not Collectable, Unknown)
 - Region 1 (Japan, Rest of the World 1)
 - Region 2 (US, EU, Japan)
 - Region 3 (US, Rest of the World 3)
 - ECOG status at baseline (0, 1)
 - Height (cm) (#)
 - Weight (kg) (#)
 - BSA (m²) (#)
 - BSA (m²) by Region 2 (#)
 - Renal function at baseline (Normal/Mild/Moderate based on Cockcroft-Gault formula)
- (#) indicates a continuous variable to be summarized.

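### SAP 8.11 closes the Cockcroft-Gault bracket after weight instead of after age; coded literally, every adult gets a negative clearance and is classed as Severe

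*SAP*

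**What the plan says.** SAP Section 8.11 states that creatinine clearance "will be calculated using well-accepted Cockcroft-Gault equation" and gives one expression for males and one for females. Both have the same numerator, which reads "140 - \text{age}[\text{years}] * \text{weight}[\text{kg" with a single pair of brackets around the whole of it. In plain notation:

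- Males: (140 - age x weight) / serum creatinine [µmol/L] x 1.228
- Females: (140 - age x weight) / serum creatinine [µmol/L] x 1.044

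Section 8.12 then says "The creatinine level/clearance will be used to identify the renal function" and instructs the programmer to "round the calculated result for the creatinine clearance to the nearest whole number before application of the table below". The classes are Normal (90 mL/min or more), Mild (60-89), Moderate (30-59) and Severe (29 or less, with no lower limit).

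Section 9.3 lists, among the baseline characteristics to be summarised, "Renal function at baseline (Normal/Mild/Moderate based on Cockcroft-Gault formula". No other visible section of the SAP or protocol gives the formula with the bracket closed after age.

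**The concern.** By ordinary operator precedence, the printed numerator is 140 minus a product that runs to hundreds or thousands for any adult. The result is then negative, which is impossible for a clearance. Because the Severe class has no lower limit, a negative value is accepted by the table instead of failing a range check. A derived variable coded exactly as specified would show every patient in both arms as severely impaired, a class that the list in Section 9.3 does not even name.

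What is at stake is a baseline description of renal function. The SAP is also the document against which derived variables are programmed and checked. If the code is right, it departs from the written rule without a record of why; if it follows the written rule, the table is wrong.

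**Working it through.** The SAP states no numerical clearance, so there is no figure to reproduce.

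**Inputs.** The formula and multipliers are from SAP 8.11, and the rounding and classes from SAP 8.12. The minimum age of 18 years (20 in Japan) and the serum creatinine limit of 1.5 mg/dL are from Protocol 8.3.1. With an assumed conversion of 88.4, that limit is 1.5 x 88.4 = 132.6 µmol/L. The documents give no patient values, so the ages, weights and creatinine values below are assumptions.

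**Step 1: sign of the printed form.** Creatinine and the multipliers are positive, so the sign depends on the numerator alone. It is negative whenever age x weight > 140:

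- at 18 years, above 140/18 = 7.8 kg
- at 20 years, above 140/20 = 7.0 kg
- at 63 years, above 140/63 = 2.2 kg

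No adult falls below these weights. This step needs only the printed formula and the entry age.

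**Step 2: one patient in full.** Age 60, 60 kg, creatinine 80 µmol/L.

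- As printed, male: (140 - 3600)/80 x 1.228 = -53.1; female: (140 - 3600)/80 x 1.044 = -45.2. Both Severe.
- Bracket after age, male: (140 - 60) x 60/80 x 1.228 = 73.7; female: (140 - 60) x 60/80 x 1.044 = 62.6. Both Mild.

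**Step 3: patients across the classes.**

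| Assumed patient | As printed | Class | Bracket after age | Class |
|---|---|---|---|---|
| Male, 20 y, 45 kg, 60 µmol/L | -15.6 | Severe | 110.5 | Normal |
| Male, 63 y, 60 kg, 80 µmol/L | -55.9 | Severe | 70.9 | Mild |
| Male, 63 y, 60 kg, 132.6 µmol/L | -33.7 | Severe | 42.8 | Moderate |
| Female, 80 y, 45 kg, 110 µmol/L | -32.8 | Severe | 25.6 | Severe |

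The last row is (140 - 3600)/110 x 1.044 = -32.8 against (140 - 80) x 45/110 x 1.044 = 25.6. This patient is inside the creatinine entry limit and is Severe under both forms.

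**Step 4: grid.** Ages 18-90, weights 30-120 kg and six creatinine values from 40 to 132.6 µmol/L give 73 x 91 x 6 = 39,858 combinations per sex. As printed, all are negative and all Severe. With the bracket after age, all four classes are filled:

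| | Normal | Mild | Moderate | Severe |
|---|---|---|---|---|
| Males | 19,191 | 9,677 | 9,372 | 1,618 |
| Females | 15,185 | 10,065 | 11,736 | 2,872 |

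These are counts of grid points, not expected patient frequencies.

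**Step 5: is only the bracket wrong?** Assuming the usual form of the equation in mg/dL (divisor 72, factor 0.85 for women), conversion to µmol/L gives 88.4/72 = 1.228 and 0.85 x 88.4/72 = 1.044. Both printed multipliers agree, so nothing else in the expression needs to change.

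**The case against.** The best counter-argument is that the intent is not in doubt. The SAP names a standard equation, gives the result in mL/min, sets ordinary clearance bands and plans a Normal/Mild/Moderate summary. A programmer would probably notice negative values in every patient. This stands as a limit on likelihood: harm arises only if the expression is coded literally. It does not make the written rule correct.

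The second argument is that the equation is typeset, and extracting text from a PDF can move a bracket. This cannot be excluded. The brackets are balanced and the two expressions agree, but they differ only in label and constant, so the same misreading could affect both. The source PDF settles it.

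A reader might infer three stronger things that the documents do not support:

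- **That every patient would be misclassified.** Every patient would be placed in Severe, but some may belong there. Eligibility limits serum creatinine, not clearance, and the 80-year-old woman in the working is eligible on that criterion with a true clearance of 25.6 mL/min.
- **That the negative values fall outside the table in Section 8.12.** They do not, since the Severe class is open below. The conflict is with the summary planned in Section 9.3.
- **That the efficacy analyses are affected.** Dosing uses body surface area (Protocol 9), stratification uses region, ECOG status and prior ramucirumab (Protocol 8.4.2), and the prognostic factors in SAP 10.4.2.2 do not include renal function. Any renal analysis in redacted text cannot be assessed and is not claimed.

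**Conclusion.** The formula is wrong as it stands in the text. Coded literally, it gives a negative clearance for every adult, places all patients in the Severe class, and makes the baseline summary in SAP 9.3 impossible to produce. Everyone whose true clearance, after rounding, is above 29 mL/min would be misclassified; how many that is depends on the patients enrolled, which the documents do not show.

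The conclusion on sign and class rests only on the printed expression, the classes in SAP 8.12 and the minimum age. The example clearances rest on assumed patient values. The whole point is conditional on the source PDF showing the same bracket.

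The importance is minor. In the visible text the derived clearance feeds one descriptive baseline row, and OS, PFS, alpha and sample size do not depend on it.

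**What to change.** 1. Compare both expressions in SAP 8.11 with the source PDF.
2. If the bracket is as printed, correct both to:
   - Males: CrCl [mL/min] = (140 - age [years]) x weight [kg] x 1.228 / serum creatinine [µmol/L]
   - Females: CrCl [mL/min] = (140 - age [years]) x weight [kg] x 1.044 / serum creatinine [µmol/L]
3. Confirm that the derivation program uses this form.

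The cost is one bracket moved in each of two lines and a short check of the code. It corrects a derived variable and changes no eligibility criterion, dose or clinical rule.

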8.12. Renal Function

The creatinine level/clearance will be used to identify the renal function. For the purpose of the present SAP the following subdivision will be used (round the calculated result for the creatinine clearance to the nearest whole number before application of the table below):

Renal Function	Creatinine Clearance (CrCl)
Normal	≥ 90 mL/min
Mild Impairment	60-89 mL/min
Moderate Impairment	30-59 mL/min
Severe Impairment	≤ 29 mL/min

8.13. Handling of Missing Data

8.13.1. Missing Efficacy Endpoints

No imputation of the missing data will be performed, unless otherwise specified, for example, censoring rules, as applicable.

8.13.2. Missing Start and Stop Dates for Prior and Concomitant Medication

Incomplete concomitant medication start and/or stop dates will be imputed as follows. If either the start of medication date is completely missing or the month and/or year of the start date is missing, the start date will be set to the first dose date. If only the day is missing, the day will be set to the first day of the month except if the start month is the same as the first dose month. If the latter is true, the start day will be set to the first dose day. No imputations will be applied to the stop date. Imputed dates will be flagged in the individual supportive subject data listings.

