9.6.2. Prior and Concomitant Medications

Prior and concomitant medications will be summarized for the AT population. The patients are summarized using counts and percentages. All concomitant medications and therapies will be coded using WhoDDE (September 2015) and summaries will use the system organ class and preferred term codes, as appropriate.

All medications, prescription and over-the-counter, from the time of signed ICF through the 30-day Safety Follow-Up Visit, will be collected and summarized in the tables. This will include any medication used to treat AEs or SAEs during the safety follow-up period. Summarization will be performed separately for prior and concomitant medications (two different tables).

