11.2.3. Missing and Partial AE Onset Dates

The start/onset dates for AEs are important for the:

1. Treatment emergent algorithm.
2. Designation of unique AE occurrences.

Completely missing or partially missing AE onset dates will be queried and every reasonable effort will be made to resolve the issue and to obtain accurate AE information from site, investigator or any other trustful source. Once all attempts of this kind has failed, the missing or partially missing AE onset date will be imputed.

The following algorithm should be used to impute adverse event start dates for which only partial information is available.

1. If onset date is completely missing or the year of the end date is missing:
 - a. Set onset date to the date of the first treatment if the end date of the AE (if available) remains sensible after imputation (i.e., imputed start date precedes end date).
 - b. Set onset date to the 1st of January of the same year as the end date is if the end date of the AE (if available) presumes that the AE ended before the first treatment of the study.
2. If (year is present and month and day are missing) or (year and day are present and month is missing):
 - a. If year = year of the first dose, then set month and day to month and day of first dose.
 - b. If year \neq year of the first dose, then set month and day to January 1st.
3. If month and year are present and day is missing:
 - a. If year and month = year and month of first dose, then set month and day to month and day of first dose.
 - b. If year and month \neq year and month of first dose, then impute the first day of the available month.

Imputed dates will be flagged in the individual supportive subject listings.

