11.5. Concomitant Medications and Anticancer Therapies

All medications will be coded using the World Health Organization Drug dictionary (WHO-DD) version SEPT2015. The therapeutic class will correspond to the second level of Anatomical Therapeutic Chemical (ATC) code corresponding to the first 3 figures.

Concomitant medications, prescribed and over the counter, that the subject takes or continues to take after the date of signed Informed Consent Form will be summarized in the table. The data will be presented by treatment group and for all treated subjects. The same subject counting procedures will also apply (e.g., major class frequencies will represent subjects only once even though the same subject can be counted for multiple minor sub-classes and generic names).

The supportive individual subject data listing will be organized displaying trade and generic drug names, start and stop dates, days relative to the start of therapy, dose, frequency, route, and indication(s).

Medications will be coded using the WHO Drug Reference List Version 2015: Q1 or higher. Prior and concomitant medications will be tabulated separately according to ATC Level III and preferred name. Chemotherapies will be further summarized according to the “regimen” (combination of individual chemotherapy medications administered in a regimen irrespective of dose, route of administration or dosing schedule). The number and percent of patients receiving granulocyte colony stimulating factor (G-CSF) will be tabulated by cycle.

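### The medication start-date rule in SAP 8.13.2 overrides a recorded year when the month is missing and never checks the imputed start against a known stop date

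*SAP*

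**What the plan says.** SAP 8.13.2 has two branches for an incomplete medication start date.

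- For a wholly missing start, and likewise when "the month and/or year of the start date is missing, the start date will be set to the first dose date".
- Where month and year are known but the day is not, the first of the month is used, unless the month is that of the first dose. In that case: "If the latter is true, the start day will be set to the first dose day".

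On stop dates it says "No imputations will be applied to the stop date", and no clause compares the imputed start with a recorded stop. It adds: "Imputed dates will be flagged in the individual supportive subject data listings". No flag is mentioned for tables.

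The dates feed several outputs. SAP 9.6.2 plans separate tables for prior and for concomitant medication, and SAP 11.5 repeats this: "Prior and concomitant medications will be tabulated separately according to ATC Level III and preferred name". SAP 11.5 also plans a listing with start and stop dates and days relative to the start of therapy, and a count of patients receiving G-CSF by cycle.

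**The concern.** An imputation rule should fill in what is unknown and leave what is known alone. Because the first branch is triggered by a missing month alone, a record that gives the year and nothing more loses the year as well. If that year is not the first-dose year, the imputed date is known to be wrong when it is assigned.

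At stake are the pre-study onset of long-standing drugs, possibly their place in the prior-medication table, and the internal consistency of the listing, where a drug could start after it ended. The SAP also treats like cases differently: its adverse-event and birth-date rules keep a known year, the medication rule does not, and no reason is given.

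**Working it through.** The plan states no figure to reproduce, so the check compares the rules and then applies them to example dates.

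**Rules side by side**

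| Known information | Medication start (SAP 8.13.2) | AE onset (SAP 11.2.3) | Birth date (SAP 8.13.4) |
|---|---|---|---|
| Year only, different from first-dose year | First-dose date | 1 January of that year (rule 2b) | 1 January of the known year |
| Year only, same as first-dose year | First-dose date | First-dose date (rule 2a) | Not applicable |
| Month and year, same as first dose | First-dose day | First-dose day (rule 3a) | Not applicable |
| Nothing | First-dose date | First-treatment date, subject to an end-date check (rule 1a) | Not applicable |

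The end-date check in AE rule 1a uses the first-treatment date only "if the end date of the AE (if available) remains sensible after imputation". Rules 2 and 3 have no such check.

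**Inputs for the examples.** All calendar dates are assumed. Cycles are 28 days (protocol 9.2.1). Study day follows SAP 8.2: difference in days, plus 1 if on or after first dose. Cycle = 1 + whole part of (days since first dose / 28). In the day-only branch, the first-dose month is read as the same month of the same year.

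**Results under SAP 8.13.2**

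1. Start 2009, month unknown, ongoing; first dose 12 September 2016. Imputed start: 12 September 2016, Study Day 1. From 1 January 2009 to first dose is 2,811 days. From 31 December 2009 it is 2,811 − 364 = 2,447 days. The imputed start is therefore 2,447 to 2,811 days late, whatever the true month. AE rule 2b would give 1 January 2009 (Study Day −2811), at most 364 days early.
2. Start 2012, month unknown, stopped 1 September 2016; same first dose. Imputed start 12 September, 12 − 1 = 11 days after the stop. AE rule 2b would give 1 January 2012, before the stop.
3. Start September 2016, day unknown, stopped 8 September; same first dose. Imputed start 12 September, 12 − 8 = 4 days after the stop. AE rule 3a gives the same impossible order.
4. G-CSF given in Cycle 3, year 2016 only, stopped 25 November 2016 (74 days after the 12 September first dose; 1 + 2 = Cycle 3). Imputed start: Day 1, Cycle 1. AE rule 2a gives the same.
5. G-CSF given in Cycle 3, year 2017 only, stopped 25 January 2017; first dose 21 November 2016 (65 days; Cycle 3). Imputed start: Day 1, Cycle 1. AE rule 2b gives 1 January 2017 (41 days, Study Day 42, Cycle 2), which is closer but still not Cycle 3.
6. G-CSF with only the day unknown, November 2016; first dose 12 September 2016. Imputed start 1 November (50 days, Cycle 2). It is not moved to Cycle 1.

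Cases 1 and 2 are repaired by keeping the known year. Cases 3 to 5 show that copying the AE rule would not be enough.

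**The case against.** The strongest reply is that little of this reaches a planned table. Several stronger readings are tempting, and the documents do not support them.

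- *Long-standing drugs are wrongly moved into the concomitant table.* SAP 11.5 counts as concomitant anything taken or continued after consent. An ongoing chronic drug is therefore in that table whether its start is 2009 or Day 1. What is lost is its onset and possibly its entry in the prior table. The visible SAP gives no date rule for prior medication, so even the second loss is only possible.
- *Every such record is misreported.* The tables count patients by drug class and name, and no visible table counts drugs begun with study drug. Onset appears mainly in the listing, where imputed dates are flagged.
- *Later G-CSF moves to Cycle 1.* This needs an unknown month or a wholly missing date, and a table that places use by start date. SAP 8.7 gives its medication cycle rule for listings only, and the detailed guidance is redacted. If use were counted from start to stop, Cycle 1 would still be wrongly included, but the method cannot be seen.
- *The AE rule always checks the end date.* Only rule 1 does. The AE rules therefore share the start-after-stop problem in the same-year and same-month branches.

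The start-after-stop error is also narrow. Medications are collected from consent (protocol 10.1.14), and screening lasts at most 28 days, with dosing due within 3 days of randomization (protocol 10.1.2). It mainly needs a drug stopped in that interval with an incomplete start.

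These limits stand. They reduce the consequences but do not remove the defect: no clause in 8.13.2 restores a known year or respects a known stop.

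**Conclusion.** The point holds as a minor defect in a descriptive convention. Read literally, SAP 8.13.2 overrides a recorded year whenever the month is missing and can produce a start after a known stop, including under the day-only branch. Where the recorded year differs from the first-dose year, the imputed date conflicts with collected data by construction.

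The effect on a single record can be large, as in case 1. The number of such records cannot be judged, because the documents do not say how many start dates lack a month. The effect on G-CSF by cycle is conditional on a step that is not visible. OS and PFS are unaffected: neither endpoint uses these medication dates, and the start of antitumor therapy has its own rule in SAP 8.13.6. The conclusion assumes that the redacted data-handling appendix does not override 8.13.2.

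**What to change.** Reword SAP 8.13.2 as follows.

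- **Year known and different from the first-dose year, month missing:** 1 January of the known year, as in SAP 11.2.3 rule 2b.
- **Year equal to the first-dose year, month missing:** first-dose date, unless a known stop date is earlier; then 1 January of that year.
- **Only the day missing, month is the first-dose month:** first-dose day, unless a known stop date is earlier; then the first of that month.
- **Start fully missing:** first-dose date, unless a known stop date is earlier; then classify the drug as prior.
- **G-CSF by cycle:** show records with an unknown start month as cycle unknown and do not assign them to Cycle 1. This is needed because cases 4 and 5 stay in the wrong cycle under the date rules alone.

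Applied to the examples, case 1 becomes 1 January 2009, case 2 becomes 1 January 2012, case 3 becomes 1 September 2016, and cases 4 and 5 are reported as cycle unknown. The cost is SAP wording, a few program lines and one extra category in the G-CSF table. No new data are needed. A 1 January date is still only accurate to the year, so the existing listing flag should stay.
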